## **Study Protocol:**

### **Background**

Earlier research findings show that when a caring encounter is established where the nurse informs the patient about the perioperative process and its proceedings and educates the patient, a significant impact on both postoperative pain and the recovery from surgery can be achieved (Bager et al. 2015, Bailey 2015, Johansson et al. 2014). Also, anxiety increases the postoperative pain and slows down the recovery from surgery (Marks 2015). An earlier investigation comparing recovery of general surgery patients to orthopedic patients showed that overall, the orthopedic patients were less recovered in the acute recovery phase as well as after one month postoperatively. The most common reason for slow recovery was pain, which was ranked high in the acute recovery phase for both orthopedic and general surgery patients. The authors state that support for the orthopedic patients must be improved (Forsberg et al. 2015).

An investigation conducted by McHugh et al. (2013) revealed that patients experience improvement in psychosocial and biomedical outcomes at six months after hip replacement. The strongest predictors of recovery were anxiety and depression, pain, previous joint surgery and taking pain medication. By recognizing these factors nurses are able to identify and provide more support for patients at risk of poor recovery after hip replacement.

Mandzuk et al. (2015) conducted a longitudinal retrospective study with total hip replacement and total knee replacement patients (N=851). The study examined self-reported quality of life and functional status over the preoperative and postoperative periods: the measurements were taken 12 months prior to surgery, one month prior to surgery and 12 months postoperatively. The results revealed that patients who had a total hip replacement tended to demonstrate higher improvement than total knee replacement patients. Male patients reported higher levels of physical and mental quality of life as well as functional status than women. Mental health scores were consistently lower in both hip replacement and knee replacement patients across the perioperative period and up to one year postoperatively compared to the reference values utilizing the SF-12 instrument (Ware et. al 1996). Thus, there is an opportunity for health care providers to proactively address the mental health of hip and knee replacement patients throughout their joint replacement trajectory. The nurses' preoperative assessment may be useful in identifying and defining patients' risk factors not only for surgery but for the entire perioperative care. The nurse's role in the preoperative assessment is that of an advocate who identifies the patient's needs and risk factors that may be affected by the surgical experience (Malley et al. 2015). The shortened hospital stays nowadays require optimizing assessment and care management by focusing on patients' greater health care needs and by tailor made care information and skills to patients' individual needs (Su et al. 2010).

This research follows a pilot study, where a new perioperative model of caring was tested with patients (n=19) undergoing a hip or a knee replacement surgery under spinal anesthesia (Pulkkinen et al. 2015). In this new model the one and same anesthesia nurse took care of the patient during the entire perioperative process (pre-, intra- and postoperative phase) and visited the patient to the surgical ward the next day after surgery. The study findings showed that the patients experienced the new model of perioperative care as beneficial. Patients experienced that they were taken seriously and that they had the opportunity to participate in their own care. They also experienced the emotional support important. Thus, the new model had influence on patient satisfaction and on the individual care. The patient safety was even

ensured; no complications or medical errors were reported concerning the patients in the study sample. The same nurse cared for the patient during the entire perioperative process, and this might have diminished the possibilities for occurring errors. For example, the reduced information transfer increases the patient safety (WHO 2007).

There are several concerns in current specialized health care that this research will address. The length of hospital stay has shortened; thus, the patients must feel safe to cope with their recovery at home. Earlier research findings show that when a caring encounter is established where the nurse educates the patient about the perioperative process has significant impact on both postoperative pain and the recovery (Bager et al. 2015, Bailey 2015, Johansson et al. 2014. Also, the new health care legislation in Finland gives the patients right to choose the place of care. Therefore, patient satisfaction is an important part of organizations' competitiveness. This research deals with a high-volume hospital service. Altogether the amount of surgical procedures performed in Finland during 2015 was 362 552 (Sjöholm/Kuntaliitto 2016). Further, the health care organizations have to deal with lack of nursing resources. This new practice may influence engagement of nurses.

### **Aim and objectives**

The aim of this study is to improve the surgical patients' care process. The objective is to explore the effect of a new perioperative practice model on 1) patient outcomes (satisfaction, surgery-related anxiety and quality of life), 2) nursing outcomes (organizational engagement), and 3) organization outcomes (timeline of surgical care process).

The study is part of [name] doc research project "Knowledge-based management in perioperative nursing". At the same time it links to professor [name]'s research projects concerning the Perioperative Dialogue.

### **Methods**

#### **Study design**

A longitudinal untreated control group design with pre- and posttests will be followed.

#### **Study sample and setting**

The study will be conducted at the Helsinki University Hospital; more specifically at the operating department K of the Peijas Hospital. The study population consist of adult female and male patients scheduled for either total hip arthroplasty (THA) or total knee arthroplasty (TKA). A control group and an experimental (intervention) group will be formed. The participants are recruited at their preoperative visits to the outpatient clinic two to three weeks prior to their scheduled operations. The inclusion criteria: 18 years of age or older, able to comprehend the study information and complete the questionnaires, and operation being performed under spinal anesthesia. One exclusion criterion for the intervention group is that the planned surgery is performed on Friday, because the postoperative visits cannot be performed during the weekend.

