## **Randomization and sample size**

Randomization of participants is performed by independent third parties (two nurse assistants at the outpatient clinic). All patients scheduled for THA and TKA attending the outpatient clinic are considered eligible and invited to participate in randomization if they meet the inclusion criteria. Eligible patients will draw one of two cards; one indicate an invitation to participate the study and the other is blank, indicating no participation in the study. Patients in the control group will be recruited every other week and patients for the intervention group every week between. This pattern will be repeated until the desired number of patients are recruited. This stratification will ensure that patients in different groups do not exchange information in the postoperative ward. The sample size requirement for comparing two means was checked with power analysis (2-sided test) with  $\alpha = 0.05$ ,  $\beta = 0.9$ , standard deviation 0.08, and differences of means 0.03 in 15D scores, which is within the slight difference of 0.015-0.035 (Alanne, Roine, Räsänen, Vainiola, & Sintonen, 2015). A sufficient sample size is determined to be 152 per group.

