## **Intervention**

Traditionally during the intra- and postoperative phases of surgical care, the patient is cared for by several nurses; i.e. by an anesthetic nurse in the operating room and by a recovery room nurse in the Post Anesthesia Care Unit (PACU). Furthermore, the pre- and postoperative visits to the surgical patients are rare in Finland; mainly due to resources and new surgical processes where patients arrive to the hospital in the morning of the scheduled procedure.

The new perioperative practice model denotes that the one and same nurse will meet the patient at his/her arrival to the operating department, and will care for the patient both in the operating room and in the PACU. Thus, the nursing care in the operating room and in the PACU remains the same but will be organized in a new way which focuses on the patient centered individual care and the continuity of care. Furthermore, the same nurse will visit the patient at the surgical unit on the first postoperative day.

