## **Data collection and Outcome Measures**

The demographic data of the participants includes age, gender, diagnosis, procedure, and ASA class (ASA Physical Status Classification 2014). Further patient data will be collected by 1) The Good Perioperative Nursing Care Scale (Leinonen & Leino-Kilpi 2001) measuring the quality of perioperative care; 2) 15D instrument measuring the health-related quality of life among adults (Sintonen 2001) and 3) STAI, the State-Trait Anxiety Inventory; measuring anxiety in adults (Spielberger et al. 2010). The schedule for patient data collection is presented in Table 1.

**Table 1.** Schedule of patient data collection

Instrument	Baseline (preoperative visit 2-3 weeks prior to surgery)	Cross-section (at discharge)	Post-test (three months after discharge)
15 D	x		x
STAI	x		x

Good Perioperative Nursing Care Scale		x	
---------------------------------------	--	---	--

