**Statistical Analysis Plan:**

Descriptive statistics will be used to present characteristics of the study participants. One- and multi-way analysis of variance will be used to compare means of groups. Interaction terms will be used to compare means of the groups defined by combinations of categorical independents. Tukey's adjustment will be used to account for multiple comparison if necessary. Statistical significance of dependencies between categorical variables are tested using Chi-square tests. SAS® statistical software, version 9.4 (SAS Institute Inc., Cary, NC, USA) will be used in statistical analysis.

In the analysis of the patient data, collected with the GPNCS, if a respondent answers to less than 50% of the quality statements, his or her response will be excluded from the analysis. Frequencies and percentages obtained with the Pearson chi-square test are calculated for the background data. Non-parametric tests are used when comparing background factors with quality categories. The reliability of the scale is checked with a Cronbach's alpha coefficient. In the analysis of data sets, the non-parametric tests will include the Kruskall-Wallis test and Mann Whitney U-test with Bonferroni corrections. A *p*-value of 0.05 is considered statistically significant.

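### Planned Friday surgery is excluded from the intervention group only, so the groups differ in eligibility and day of surgery may bias the comparison

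*Combined protocol and SAP*

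**What the plan says.** The inclusion criteria under Study sample and setting apply to everyone. The section then adds a restriction for one group: "One exclusion criterion for the intervention group is that the planned surgery is performed on Friday", with the reason "because the postoperative visits cannot be performed during the weekend". The Intervention section shows which component drives this: "the same nurse will visit the patient at the surgical unit on the first postoperative day".

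Under Randomization and sample size, THA and TKA patients at the clinic "are considered eligible and invited to participate in randomization if they meet the inclusion criteria". No Friday rule for controls appears there or anywhere else. The card draw settles only whether a patient is invited: "one indicate an invitation to participate the study and the other is blank, indicating no participation in the study". The group follows from alternating recruitment weeks.

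On data, the protocol says "The demographic data of the participants includes age, gender, diagnosis, procedure, and ASA class"; weekday of surgery is not listed. On analysis, the SAP says "One- and multi-way analysis of variance will be used to compare means of groups". It names no weekday factor, restriction or sensitivity analysis.

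**The concern.** An eligibility rule applied to one group and not the other makes the groups differ by design. Here the intervention group can hold only patients with no planned Friday surgery, while the control group can hold patients from every operating day. The stated reason explains why a Friday patient cannot receive the full practice model. It does not explain why such a patient should serve as a comparator.

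Friday controls have their first postoperative day on a Saturday, and Friday lists may carry a different mix of cases. If either is related to outcome, part of any group difference reflects who was eligible rather than the practice model. A larger sample does not remove that. The care-quality scale is the more plausible exposure, because it is completed at discharge, on average on the third postoperative day, and so describes a stay that for Friday controls spans the weekend. For the three-month change in 15D the effect may be small or nil. The plan as written contains no analysis that would show which.

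**Working it through.** **Inputs from the protocol (Randomization and sample size).** Two-sided α = 0.05; SD 0.08; target difference 0.03 in 15D; 152 per group; 0.015 to 0.035 as the range regarded as slight. The 0.9 printed as β reproduces the sample size only when read as power.

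**Reproducing the plan's figure.** n per group = 2 × [0.08 × (1.960 + 1.2816) / 0.03]² = 149.4, so 150. A t-based calculation gives 151. The stated 152 is consistent with both, and its power by the normal approximation is 90.5%. The sample size is not the problem.

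**Assumptions, not in the documents.** Let f be the Friday share of controls and d the difference in mean outcome between Friday and other-day controls. I take f = 20% (an even spread over five operating days), with a range of 10% to 25%, and let d start at zero.

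**Imbalance.** 152 × 0.20 ≈ 30 Friday controls against 0 in the intervention group (152 × 0.10 ≈ 15; 152 × 0.25 = 38).

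**Bias and false-positive rate.** Size of bias b = f × d; its direction is unknown. SE = 0.08 × √(2/152) = 0.00918. Two-sided false-positive rate = Φ(−1.96 + b/SE) + Φ(−1.96 − b/SE).

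15D, f = 20%:

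| d | b | b / 0.03 | False-positive rate |
|---|---|---|---|
| 0 | 0 | 0% | 5.0% |
| 0.01 | 0.002 | 7% | about 5.5% |
| 0.015 | 0.003 | 10% | 6.2% |
| 0.035 | 0.007 | 23% | 11.9% |

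If the bias opposes a true difference of 0.03, power = Φ((0.03 − b)/SE − 1.96). This falls from 90.5% to 83.7% at d = 0.015 and to 70.8% at d = 0.035. Across f = 10% to 25% and d = 0.01 to 0.035, b runs from 0.001 to 0.00875 (3% to 29% of the target) and the false-positive rate from 5.1% to 15.9%.

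**Care-quality scale.** No SD is given, so I work in SD units: SE = √(2/152) = 0.1147. At f = 20%, Friday effects of 0, 0.2 and 0.5 SD (assumed) give biases of 0, 0.04 and 0.10 SD and false-positive rates of 5%, 6.4% and 14.1%.

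**Does anything else in the design remove it?** No. The card draw does not set the group, and alternating recruitment weeks do not affect which weekdays are eligible. Even a proper randomisation would not balance a criterion applied to one group after the fact. A weekday term in the ANOVA would help only in part: with no Friday intervention patients, a Friday effect in that group cannot be estimated.

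**The case against.** The strongest reply is that no harm is shown. The Friday share, the Friday effect and the care-scale SD are all assumed. The middle 15D scenarios move the error rate only from 5% to about 5.5–6.2%. The 11.9% figure needs a Friday effect of 0.035, larger than the 0.03 the trial is powered to detect, and the 14.1% figure concerns a secondary outcome. This stands: those two figures are extremes, not expectations. The primary outcome is also a change from baseline, so a stable Friday difference in 15D level would largely cancel, leaving only a difference in change. That stands too, but it does not help the care-quality scale, which has no baseline measurement.

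Three points are right but do not alter the conclusion. First, the intervention's eligible patients are a subset of the controls' rather than a separate population. Second, the general eligibility sentence covers both groups, so Friday eligibility for controls rests on the absence of any rule against it. If controls were in practice also limited to other days, the protocol should say so. Third, the surgery date must be known to the study, so weekday could be derived; but no analysis uses it, and the SAP names no specific factors for its multi-way ANOVA at all.

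It is also fair that allocation by recruitment week is a separate problem that this fix would leave in place. Finally, a Monday–Thursday sensitivity analysis alone would reveal a Friday influence without slowing recruitment, but it would leave the primary comparison unmatched. Restriction does narrow the population, but only to the patients to whom the full model can be delivered.

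**Conclusion.** The concern holds. The unequal eligibility is certain from the text, and nothing in the design or the SAP corrects it. Whether it biases the results cannot be determined from the documents. With no Friday effect there is no bias. At an assumed 20% share, a Friday effect within the range the protocol itself calls slight (0.015 to 0.035) would shift the 15D comparison by 0.003 to 0.007, or 10% to 23% of the target. The care-quality scale is more exposed. This should be fixed because the remedy is cheap, not because serious bias has been shown.

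**What to change.** Apply the planned-Friday exclusion to both groups, record the planned surgery weekday at recruitment, and keep 152 per group. If Friday controls are already enrolled, prespecify the primary comparison on patients with planned Monday–Thursday surgery, and report all controls in a sensitivity analysis. Classify patients by the date set before surgery, so that later rescheduling cannot move them in or out.

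The cost is one sentence in the eligibility criteria and one recorded variable. Control recruitment slows: keeping 152 at a 20% Friday share uses up the flow that would otherwise have yielded 152/0.80 = 190 enrolled all-weekday controls (152/0.90 ≈ 169 to 152/0.75 ≈ 203 at 10% to 25%). These are enrolled patients, not patients approached before the card draw.

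If enrolled Friday controls are left out of the primary comparison without replacement, 122 face 152 at a 20% share: SE = 0.08 × √(1/122 + 1/152) = 0.00972, and power for 0.03 falls from 90.5% to about 87%. At shares of 10% and 25% (137 and 114 controls) it is 88.9% and 85.7%.

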## **Randomization and sample size**

Randomization of participants is performed by independent third parties (two nurse assistants at the outpatient clinic). All patients scheduled for THA and TKA attending the outpatient clinic are considered eligible and invited to participate in randomization if they meet the inclusion criteria. Eligible patients will draw one of two cards; one indicate an invitation to participate the study and the other is blank, indicating no participation in the study. Patients in the control group will be recruited every other week and patients for the intervention group every week between. This pattern will be repeated until the desired number of patients are recruited. This stratification will ensure that patients in different groups do not exchange information in the postoperative ward. The sample size requirement for comparing two means was checked with power analysis (2-sided test) with  $\alpha = 0.05$ ,  $\beta = 0.9$ , standard deviation 0.08, and differences of means 0.03 in 15D scores, which is within the slight difference of 0.015-0.035 (Alanne, Roine, Räsänen, Vainiola, & Sintonen, 2015). A sufficient sample size is determined to be 152 per group.

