### **Primary Outcome Measures**

1. Change from baseline Health Related Quality of Life (HRQoL) at three months after the surgical procedure. Time Frame: Baseline 2-3 weeks prior to, and post-measurement 3 months after the procedure (The 15D instrument)

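### The card draw selects who is invited, not who gets the intervention: group follows alternating weeks, so the allocation is not randomized and the SAP names no adjustment for it

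*Combined protocol and SAP*

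**What the plan says.** The protocol section Randomization and sample size states that independent third parties, two nurse assistants at the outpatient clinic, randomize the participants. The mechanism is: "Eligible patients will draw one of two cards; one indicate an invitation to participate the study and the other is blank". The blank card means that the patient does not take part.

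Group membership is set by a separate rule: "Patients in the control group will be recruited every other week and patients for the intervention group every week between". The order is fixed: "This pattern will be repeated until the desired number of patients are recruited". The reason given is that patients of the two groups should not exchange information on the postoperative ward.

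The Study design section does not use the word randomized: "A longitudinal untreated control group design with pre- and posttests will be followed". Study sample and setting adds a rule that applies to one group only: "One exclusion criterion for the intervention group is that the planned surgery is performed on Friday".

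The primary outcome is "Change from baseline Health Related Quality of Life (HRQoL) at three months after the surgical procedure", measured by the 15D. For group comparisons the SAP says: "One- and multi-way analysis of variance will be used to compare means of groups". It also mentions interactions among categorical factors but does not say which factors. Baseline 15D, prognostic variables, surgery weekday and recruitment week are not named.

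**The concern.** A section that speaks of randomization leads the reader to credit the comparison with balance by chance and an unforeseeable assignment. A draw between invitation and blank gives neither. It decides which eligible patients enter the study, and the calendar then decides the group.

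A strict week-on, week-off pattern can be foreseen by anyone who knows it. Booking into clinic weeks, judgement of eligibility, the decision to consent and the self-reported baseline scores are therefore all open to influence by knowledge of the group. Patients may also learn their group before consenting. The Friday rule makes the eligible populations differ even if none of this happens.

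At stake is whether a difference in 15D change can be attributed to the practice model or only to who entered in which weeks. The SAP as written names nothing to separate the two.

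**Working it through.** **Step 1. What chance decides.** The draw has two outcomes, invited or not taking part. Neither is control or intervention. Group is then a function of the recruitment week. Number of patients assigned a group by chance: 0 of 2 × 152 = 304. Whole-week blocks may be reasonable for keeping the groups apart on the ward, but that reason does not require a fixed order of blocks.

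**Step 2. The plan's sample size.** Inputs from Randomization and sample size: two-sided α 0.05, SD 0.08, difference 0.03, and 0.9 (written as β, but it reproduces only as power).

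- n per group = 2 × (0.08/0.03)² × (1.960 + 1.282)² ≈ 150; the t-test version gives 151. The stated 152 is reproduced.
- SE = 0.08 × √(2/152) = 0.00918; power at 152 = Φ(0.03/0.00918 − 1.96) = 0.905.

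The calculation treats patients as independent and makes no allowance for allocation by week. The steps below take 0.08 as the SD of the analysed outcome.

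**Step 3. How sensitive the test is to a non-treatment difference.** For a systematic group difference b in the analysed outcome, type I error = 1 − Φ(1.96 − b/SE) + Φ(−1.96 − b/SE). The values of b are assumed.

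| b | Type I error |
|---|---|
| 0.005 | 0.085 |
| 0.010 | 0.193 |
| 0.015 | 0.373 |

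**Step 4. The Friday rule.** The documents do not give the share of surgeries on Friday; 10–20% is assumed.

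- Friday patients among controls: 152 × 0.10 ≈ 15 to 152 × 0.20 ≈ 30; among intervention patients: 0.
- For this alone to shift the comparison by 0.015 (half the target), Friday patients' mean change would have to differ from the others' by 0.015/0.10 = 0.15 or 0.015/0.20 = 0.075. That is 5 or 2.5 times the target difference, so the effect of this rule alone is probably modest.

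**Step 5. Weeks as clusters.** Assumed: 10 patients enrolled per week and within-week correlation (ICC) 0.01–0.05. Design effect DE = 1 + (10 − 1) × ICC. Type I error if weeks are ignored = 2 × [1 − Φ(1.96/√DE)].

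| ICC | DE | Type I error, week ignored | Power at 152, week modelled | n per group needed |
|---|---|---|---|---|
| 0.01 | 1.09 | 0.061 | 0.879 | 152 × 1.09 → 166 |
| 0.05 | 1.45 | 0.104 | 0.775 | 152 × 1.45 → 221 |

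The SAP names no week term, so the type I error column describes the plan as written. The power column is the price of correcting it.

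**The case against.** The strongest reply is that the protocol is open about what it does. Study design claims only an untreated control group with pre- and post-tests, the alternation is stated plainly and it has a reason. A non-randomized design is not in itself an error. Multi-way analysis of variance could hold age, gender, procedure or ASA class, all of which are collected, and analysing change removes a constant baseline difference in 15D. The card draw by third parties limits hand-picking within a week. The figures for bias, clustering and Friday share rest on assumptions, and the Friday effect is small by its own arithmetic.

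Much of this is fair, and it narrows the point without removing it. The design may stand if it is called what it is. Factors that could be included but are not named can be chosen after the data are seen. Change scores leave regression to the mean, differences in recovery by procedure or ASA class, and week effects. The card draw cannot balance the groups across weeks. The figures show scale only; the conclusion rests on the allocation text.

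One further objection adds to the concern. Recruitment takes place two to three weeks before surgery. A control recruited in week 1 is operated on in week 3 or 4, and an intervention patient recruited in week 2 in week 4 or 5. Both can be on the ward in week 4, so alternating recruitment weeks does not guarantee the separation that justifies it. Randomizing the order of recruitment weeks would not cure that either.

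**Conclusion.** The point holds. The allocation is systematic, by alternating week, and the label of randomization claims a property that the described procedure does not have. Eligibility differs between the groups by design, and the SAP specifies no adjustment for baseline, prognosis or week. This must be corrected, because the allocation determines whether a difference in the primary outcome can be read as causal.

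The certain part comes from the text: 0 of 304 patients are allocated by chance. The numerical consequences are conditional on the assumed bias sizes, weekly enrolment, ICC and Friday share. The documents do not show that bias occurred.

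**What to change.** **Wording.** Describe the study as a non-randomized alternating-week comparison and the card draw as random sampling of eligible patients. This costs only text. The document lists a publication address for the study, so the same description may be needed in reports.

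**Primary analysis.** Prespecify an ANCOVA of 3-month 15D (or its change) on group, adjusted for baseline 15D, procedure, age, gender and ASA class, with a random effect for recruitment week. The covariates are already collected; recruitment week and surgery weekday must be kept in the dataset. Surgery week is worth keeping too, given the possible overlap on the ward. If outcome data have already been seen, say so when reporting the model. Accounting for week costs the precision shown in Step 5; baseline adjustment may recover part of it. Adjustment cannot remove unmeasured confounding, so the wording has to change as well.

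**Friday eligibility.** Reconcile the rule so that the primary comparison uses the same eligibility in both groups, for example by leaving Friday-surgery controls out of it. With an assumed 10–20% share, 152 − 15 = 137 to 152 − 30 = 122 controls remain. Power = Φ(0.03/[0.08 × √(1/152 + 1/n)] − 1.96) is then about 89% to 87%, before any allowance for week. Keeping 152 analysed controls would mean enrolling 152/0.9 ≈ 169 to 152/0.8 = 190.

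**Only if recruitment has not started.** Randomize the order of whole weeks from a list held outside the clinic, withhold the group from clinic staff until that week's recruitment closes, apply common eligibility and keep week in the analysis. The cost is less regular nurse rosters.

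### The alternating recruitment week sets each patient's group, but the sample size and the ANOVA treat patients as independent; irregular variation in 15D change between recruitment weeks would push type I error above 5%.

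*Combined protocol and SAP*

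**What the plan says.** **Allocation** (protocol, *Randomization and sample size*). The card draw governs entry only: "Eligible patients will draw one of two cards; one indicate an invitation to participate the study and the other is blank". The group follows from the week of recruitment: "Patients in the control group will be recruited every other week and patients for the intervention group every week between". The cycle has no fixed length: "This pattern will be repeated until the desired number of patients are recruited". The stated reason for alternating is to stop patients in different groups from exchanging information on the ward.

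**Sample size** (same section). A two-sided comparison of two means at alpha 0.05, with 0.9 printed as beta, uses "standard deviation 0.08, and differences of means 0.03 in 15D scores". The result: "A sufficient sample size is determined to be 152 per group". No ICC, design effect, number of weeks or number of patients per week is given.

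**Outcome and timing.** The primary outcome is "Change from baseline Health Related Quality of Life (HRQoL) at three months after the surgical procedure". The 15D is first measured at "Baseline (preoperative visit 2-3 weeks prior to surgery").

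**Analysis** (SAP): "One- and multi-way analysis of variance will be used to compare means of groups". The SAP adds interaction terms, Tukey's adjustment, chi-square tests and rank tests. It names no random week effect, week-level analysis or cluster-robust variance.

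**The concern.** No patient is individually randomised to an arm. All patients recruited in a given week belong to the same arm, so the week is the unit of assignment. A patient-level ANOVA is valid only if change in 15D has no irregular variation between recruitment weeks. The plan neither states that assumption nor provides a check.

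If such variation exists, each week's deviation falls on one arm. The ANOVA's standard error leaves that out, so its p-values are too small. A chance difference between control weeks and intervention weeks could then be reported as an effect of the new practice model on the primary outcome. The target difference of 0.03 is small against an SD of 0.08.

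The multi-way option in the SAP does not solve this. Each week lies wholly within one arm, so a fixed week factor would be aliased with group.

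**Working it through.** **1. The plan's own figure.** Inputs from *Randomization and sample size*: difference 0.03, SD 0.08, two-sided alpha 0.05, and 0.9 read as power.

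n = 2 × (1.96 + 1.2816)² × (0.08/0.03)² = 149.4, so 150 per group. The t-test version needs 151, and 152 gives 90.3% power. Power of 0.80 would give 112, and a one-sided test 122. The stated 152 is therefore the independent-patients figure, with a design effect of 1.

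**2. Variation tied to the recruitment week.** Let m be the patients per week (both arms use the same m). All values of m and ICC here are assumptions.

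Design effect DE = 1 + (m − 1) × ICC. Actual type I error = 2 × [1 − Φ(1.96/√DE)].

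| Case | m | ICC | DE | Type I error | Simulated (20,000 trials) |
|---|---|---|---|---|---|
| A | 5 | 0.01 | 1.04 | 5.5% | 5.2% |
| B | 10 | 0.02 | 1.18 | 7.1% | 6.9% |
| C | 15 | 0.05 | 1.70 | 13.3% | 13.3% |

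With ICC 0 the error is 5.0%.

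**3. Variation tied to the surgery week.** Surgery follows recruitment by two to three weeks. Suppose a share p of patients wait two weeks and the rest three. A surgery week then holds patients of both arms, and its shared effect partly cancels. The factor that replaces DE is

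1 − ICC + ICC × [m(2p − 1)² + 2p(1 − p)].

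- p = 1: this returns the DE above.
- p = 0.5: it is 1 − ICC/2, that is 0.995, 0.99 and 0.975, so there is no inflation. Simulations gave 4.8% to 5.6% across A, B and C.
- p = 0.9: 1.024, 1.112 and 1.439, giving 5.3%, 6.3% and 10.2%. Simulations gave 5.1-5.4%, 6.1-6.5% and 10.3-10.5%.

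**4. Smooth calendar drift** (simulated, linear/seasonal).

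| Case | Patient-level ANOVA | Week means | Week means with 3-df time term |
|---|---|---|---|
| B | 5.0/4.7% | 3.4/3.2% | 5.2/5.1% |
| C | 5.5/4.7% | 1.1/0.9% | 5.0/5.0% |

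Alternation largely balances drift for the ANOVA. A week-level analysis becomes conservative unless it includes a time term.

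**5. Power of a week-based analysis at 152 per group.** Reading 0.08 as the SD of the analysed quantity, with df = 2(152/m − 1) and no baseline: 88%, 83% and 66% in A, B and C.

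With baseline 15D and a 3-df time term, power depends on the baseline correlation r (assumed) and on what 0.08 measures. The residual SD is 0.08√(1 − r²) if 0.08 is the score SD, or 0.08√((1 + r)/2) if it is the change SD. The same ICC is assumed for the residual. Entries are score SD / change SD; the two readings coincide at r = 0.5.

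| Case | r = 0.3 | r = 0.5 | r = 0.7 |
|---|---|---|---|
| A | 91/97% | 95% | 99/93% |
| B | 86/95% | 92% | 98/88% |
| C | 69/83% | 77% | 91/72% |

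The reading of 0.08 matters for the planned ANOVA too. If it is the score SD, the change has SD 0.08√(2(1 − r)). Power with independent patients is then 79% at r = 0.3, 90% at r = 0.5 and 99% at r = 0.7.

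**The case against.** **Staffing and operating lists belong to the surgery week, not the recruitment week.** This stands. Step 3 shows that such disturbances barely inflate the error when waits mix evenly, and approach the step 2 figures only when nearly all patients share one wait. A reader might infer that every week-to-week disturbance falls wholly on one arm. The documents do not support that.

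**Change from baseline already removes stable differences in case mix.** This stands in part. Differences between weeks in 15D level drop out; differences in expected improvement do not.

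**The size rests on assumption.** True. The documents give no ICC or patients per week, nothing in them shows that 15D at three months clusters by clinic week, and cases A to C raise both quantities together, which widens the range. In case A the simulated 5.2% is hardly distinguishable from 5%.

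**Drift is not perfectly harmless.** The 5.5% for linear drift in case C is as large as the case A inflation, so drift is largely, not exactly, balanced.

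**A sensitivity analysis would be enough.** This is arguable, since the adjusted model costs degrees of freedom. But the primary analysis should respect the unit that assigned the group, and baseline 15D is already collected. An elaborate specification is not needed.

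**Conclusion.** The concern holds conditionally and is a recommended improvement, not a fatal flaw. Three facts are firm: recruitment week sets the group, 152 per group reproduces only for independent patients, and the SAP names no analysis that reflects the week.

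The consequence depends on irregular variation in 15D change by recruitment week. If there is none, the planned ANOVA is sound. If there is, type I error is about 5.5%, 7.1% or 13.3% in the three assumed cases. These are upper ends for the stated m and ICC, because surgery-week effects are at least partly shared when waits differ. They are not bounds over all possible ICCs.

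A reader might also infer that the trial's type I error is known to be inflated, or that enrolment must rise. Neither follows, because the documents give no ICC, and baseline adjustment can recover some or all of the lost power in A and B (only part in most of C). Nothing is concluded here about patients who share a nurse; a week term does not address that.

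**What to change.** 1. **Primary 15D analysis.** Model change in 15D on group and baseline 15D, with a simple calendar-time term, a random effect for recruitment week and Kenward-Roger degrees of freedom. An equivalent analysis of week means would also serve. The time term is there because week-level analysis is conservative under drift.
2. **Sensitivity analysis.** Report the patient-level ANOVA alongside.
3. **Data.** Record each patient's recruitment week. *Data collection and Outcome Measures* does not list it, although the allocation depends on it.
4. **Sample size text.** Restate as: *power (1 − beta) = 0.90 for 152 analysable, independent patients per group, without baseline adjustment*. Say whether SD 0.08 is for the score or the change, and give the power of the adjusted model under a stated ICC and number of patients per week.

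**Cost.** No added enrolment, and one extra recorded item. Degrees of freedom fall, for example from 302 to about 25 in case B (2 × (15.2 − 1) − 3 = 25.4). If there is no week variation, at 10 patients per week, the week-level analysis with the time term and no baseline has 87.8% power against 90.2%, a loss of about 2 points that baseline adjustment largely offsets. If week variation is large, intervals widen: in case C by 14% to 30% against the ANOVA of change (r = 0.3 to 0.7), where the ANOVA's interval is itself too narrow.
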